Physical Examination	X	Physical examination (including body weight) will report findings in the irradiated area during Short- and Long-Term FU periods.
ECOG PS	X	
Adverse Event Assessment	X	Evaluation of ongoing or new AEs assessed as related to study intervention until resolution or permanent outcome. New SAE assessed as unrelated to study intervention only up to Wk 27.
Concomitant Therapy	X	
Adjuvant Chemotherapy	X	Adjuvant chemotherapy if given, according to local guidelines, must start between 1 and 3 mo after surgery.
Hematology	X	
Serum Chemistry and Coagulation	X	

Study Periods	Long-term Safety FU	Notes
Visit Weeks	19 to 52	
Visit Week	21 and 27 wk after start of study intervention/ randomization: Wk 21 and 27; thereafter every 3 mo in Yr 1: Wk 39 and 52	Participants followed-up until 1 year after start of study intervention/randomization, or earlier due to any reason whereby tumor assessments are no longer applicable (e.g. if new treatment is started, study discontinued, withdrawal of consent). Adjuvant chemotherapy is allowed as per local standards (see Section 6.5). Participants receiving adjuvant chemotherapy will continue to follow the schedule of activities as per protocol. If adjuvant chemotherapy is given any additional safety evaluations/laboratory tests will be as per local practice. Reason for early discontinuation should be captured in source documents. If EOT occurs before Wk 52, all assessments must be done as planned for Wk 52.
Visit Windows (Week)	± 1 for Wk 21; ± 2 for other visits	

Participants who have already been followed up for more than 1 year (Long-term Safety or Survival Follow-up) will be discontinued from the study after the approval of protocol amendment version 4.0 by the respective Health Authority and Ethics Boards. Participants will be informed of the discontinuation by the Investigator via a phone call. No further study visits or assessments are planned.

Assessment and Procedures

Carcinoembryonic Antigen	X	
CCI		
MRI/CT	X (starting Wk 27)	T ₂ weighted and diffusion weighted, without gadolinium. No MRI/CT at Wk 21.

AE=adverse event, CT=computerized tomography, ctDNA=circulating tumor DNA, DBP=diastolic blood pressure, ECOG PS=Eastern Cooperative Oncology Group Performance Status, EOT=End of Trial, FU=Follow-up, MRI=magnetic resonance imaging, SAE=serious adverse event, SBP=systolic blood pressure.

CCI

Table 4 Pharmacokinetic Sampling Schedule of Peposertib and Capecitabine

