4.1.3 Follow-up Periods

The study follow-up will include:

- **Short-term Safety Follow-up:** the duration of the Short-term Safety Follow-up is approximately 13.5 to 14 weeks after treatment completion, including 30 days after surgery, with an optional 1 visit per week from Week 7 to Week 14 in case of acute toxicities until recovery to Grade 1 or to baseline. For all participants, a mandatory visit will be performed at Week 14, approximately 1 to 2 weeks prior to surgery, including a tumor assessment with MRI (T_2 weighted and diffusion weighted) needed for restaging and evaluation. Additional details on tumor evaluation methods and response assessments are provided in Section 8.1.2.
- Surgical intervention must be performed 15 weeks (\pm 14 days) after start of study intervention/randomization (i.e. approximately 9.5 weeks after stopping RT), unless there are contraindications for surgery, or if the participant refuses. The last Short-term Safety Follow-up visit is scheduled for Week 19, approximately 4 to 6 weeks after surgical intervention/imaging/biopsy, as per SoC. During this visit, all safety information since the last visit, including surgical and/or biopsy morbidities/toxicities will be collected.
- **Long-term Safety Follow-up:** participants will be followed-up at 21 and 27 weeks after start of study intervention/randomization; every 3 months until 1 year after start of study intervention/randomization. Details on tumor evaluation methods and response assessments are provided in Section 8.1.2. Adjuvant chemotherapy is allowed as per local standards (see Section 6.5). Participants receiving adjuvant chemotherapy will continue to follow the schedule of activities (SoA) as per protocol. If adjuvant chemotherapy is given, any additional safety evaluations/laboratory tests will be as per local practice.
- Participants who have already been followed up for more than 1 year (Long-term Safety or Survival Follow-up) will be discontinued from the study after the approval of protocol amendment version 4.0 by the respective Health Authority and Ethics Boards. Participants will be informed of the discontinuation by the Investigator via a phone call. No further study visits or assessments are planned.

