6.5 Concomitant Therapy

- Adjuvant chemotherapy is allowed during the Long-term Safety Follow-up period if initiated within 1 to 3 months after surgery. The following adjuvant chemotherapies are allowed: FOLFOX and CAPEOX or capecitabine as per NCCN 2019 guidance.
- Drugs mainly metabolized by CYP3A with a narrow therapeutic index are to be used with caution. Examples of drugs are found on the following page: <https://www.fda.gov/Drugs/DevelopmentApprovalProcess/DevelopmentResources/DrugInteractionsLabeling/ucm093664.htm>. The Investigator may decide not to include a participant in the study, if the participant cannot withdraw the drugs that have a narrow therapeutic index and that are known to be metabolized via CYP3A; if the Investigator decides to enroll a participant who is treated with one of these drugs, close safety monitoring is advised.
- Record in the electronic Case Report Form (eCRF) all concomitant therapies (e.g. medicines or nondrug interventions) used from the time the participant signs the informed consent until completion of the study, including any changes. For prescription and over-the-counter medicines, record the name, reason for use, dates administered, and dosing information.

Contact the Medical Monitor for any questions on concomitant or prior therapy.

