- Grade 5 or Death.

Any clinical AE with severity of Grade 4 or 5 must also be reported as an SAE. However, a laboratory abnormality of Grade 4, such as anemia or neutropenia, is considered serious only if the condition meets one of the serious criteria specified below.

If death occurs, the primary cause of death or event leading to death should be recorded and reported as an SAE. "Fatal" will be recorded as the outcome of this specific event and death will not be recorded as separate event. Only, if no cause of death can be reported (e.g. sudden death, unexplained death), the death per se might then be reported as an SAE.

Investigators must also systematically assess the causal relationship of AEs to study intervention (including any other nonstudy interventions, radiation therapy) using the following definitions. Decisive factors for the assessment of causal relationship of an AE to the study intervention include, but may not be limited to, temporal relationship between the AE and the study intervention, known side effects of study intervention, medical history, concomitant medication, course of the underlying disease, and study procedures.

Unrelated: Not reasonably related to the study intervention. AE could not medically (pharmacologically/clinically) be attributed to the study intervention under study in this clinical study protocol. A reasonable alternative explanation must be available.

Related: Reasonably related to the study intervention. AE could medically (pharmacologically/clinically) be attributed to the study intervention under study in this clinical study protocol.

Abnormal Laboratory Findings and Other Abnormal Investigational Findings

Abnormal laboratory findings and other abnormal investigational findings (e.g. on an ECG trace) should not be reported as AEs unless they are associated with clinical signs and symptoms, lead to study intervention discontinuation or are considered otherwise medically important by the Investigator. If a laboratory abnormality fulfills these criteria, the identified medical condition (e.g. anemia or increased alanine aminotransferase) must be reported as the AE rather than the abnormal value itself.

Serious Adverse Events

An SAE is any untoward medical occurrence that at any dose:

- Results in death

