Concomitant procedures are procedures other than study medications and pre medications for study drug, which started prior to first dose date of study treatment and continued during the on treatment period as well as those started during the on treatment period. These will be listed according to the CRF page “Concomitant Procedures”. Procedures started after the on treatment period will be presented and flagged in listing.

In case the date values will not allow unequivocal allocation of a procedure to concomitant procedure, the procedure will be considered as concomitant procedure (see Section 0 for incomplete or missing dates).

The listing will include: dose level, subject identification number and all collected data-fields on the corresponding eCRF page.

12.4

Subsequent Anti-cancer Treatment

Subsequent anti-cancer treatments will be listed according to eCRF pages “Anti-cancer treatment after discontinuation”, “Surgery after discontinuation” and “Anti-cancer radiotherapies after discontinuation”. The listings will include: dose level, subject identification number and all collected data-fields on the corresponding eCRF pages. Name of the anti-cancer RT will be tabulated as given from the most recent available version of WHO-DD .

In addition, participants who underwent rectal surgery after Week 15 will be listed according to eCRF page “Rectal surgery after Week 15 details”. This listing will include: dose level, subject identification number and all collected data fields on the corresponding eCRF page.

13

Treatment Compliance and Exposure

Population: SAF analysis set

Treatment compliance and exposure will be listed and summarized by dose level and overall using the SAF analysis set.

All dosing calculations and summaries will be based on “M3814 (PEPOSERTIB)/PLACEBO Administration”, “Radiotherapy Administration” and “Capecitabine Administration” eCRF pages.

In the Phase Ib part, participants will be assigned peposertib given in combination with capecitabine 825 mg/m² twice daily 5 days/week. The starting dose of peposertib for the first cohort will be 50 mg once daily 5 days/week. The planned dose of RT to the tumor area is

- 50 Gy with a schedule of 25 days and
- 50.4 Gy with a schedule of 28 days

For the calculations, only doses > 0 will be taken into account if not otherwise specified.

Treatment duration

The duration of peposertib treatment (in weeks) during the study is defined as :

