15.2.3 Late Toxicities

A number of outputs will be produced for late adverse events. An adverse event is defined as a late toxicity if it starts after the on-treatment period, and it meets one of the following criteria:

- It is the first occurrence of adverse event for this participant on MedDRA preferred term level
- It is a recurring adverse event but there is gap between the end date of the previous occurrence and the start date of the re-occurrence (start date of re-occurrence – end date of previous occurrence > 0)
- It is a recurring adverse event and there is no gap between the end date of the previous occurrence and the start date of the re-occurrence, and the grade has worsened.

The following outputs will be produced for late toxicities:

- Table of all late toxicities by worst CTCAE grades: any grade (including AEs with missing grade), grades ≥ 3 , ≥ 4 and 5
- Listing of all late toxicities related to any trial treatment
- Listing of all late toxicities grade ≥ 3

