15.4 Clinical Laboratory Evaluation

Population: SAF analysis set

Listings and summaries by visit will include all assessments, whereas shift tables and summaries of worst on-treatment values will not consider assessments after the on-treatment period.

Local laboratory values (including corresponding normal ranges) will be presented in summary statistics, shift tables and boxplots. In addition, liver toxicity will be assessed with Hy's Law analysis.

Laboratory results will be classified according to the NCI-CTCAE version 5.0. Additional laboratory results that are not part of NCI-CTCAE will be presented according to the categories: below normal limits, within normal limits and above normal limits (according to the laboratory normal ranges).

Common Terminology Criteria (CTC) gradable parameters

In this trial, Common Terminology Criteria (CTC) gradable parameters are the following:

Table 11 Common Terminology Criteria (CTC) gradable parameters

Category	Parameter (LBTEST)	Parameter code (LBTESTCD)	Name in NCI-CTC version 5.0	Direction of abnormality
Clinical Chemistry				
Electrolytes	Calcium	CA	Hypocalcemia/Hypercalcemia	Low/High
Electrolytes	Magnesium	MG	Hypomagnesemia/Hypermagnesemia	Low/High
Electrolytes	Potassium	K	Hypokalemia/Hyperkalemia	Low/High
Electrolytes	Sodium	SODIUM	Hyponatremia/Hypernatremia	Low/High
Enzymes/cardial	Creatine phosphokinase (CPK)	CK	CPK increased	High
Enzymes/liver	Alanine aminotransferase	ALT	Alanine aminotransferase increased	High
Enzymes/liver	Alkaline phosphatase	ALP	Alkaline phosphatase increased	High
Enzymes/liver	Aspartate aminotransferase	AST	Aspartate aminotransferase increased	High
Enzymes/liver	Total bilirubin	TBILI	Blood bilirubin increased	High
Metabolism	Glucose	GLUC	Hypoglycemia	Low
Metabolism	Uric acid ⁽¹⁾	URATE	Hyperuricemia	High
Plasma proteins	Albumin	ALB	Hypoalbuminemia	Low
Renal/kidney	Creatinine	CREAT	Creatinine increased	High
Renal/kidney	Creatinine clearance	CREATCLR	Chronic kidney disease	Low
Enzymes/cardial	Lactate dehydrogenase	LDH	Lactate dehydrogenase increased	High
Coagulation	Activated partial thromboplastin time	APTT	Activated partial thromboplastin time prolonged	High
Coagulation	International normalized ratio (INR)	INR	INR increased	High

Category	Parameter (LBTEST)	Parameter code (LBTESTCD)	Name in NCI-CTC version 5.0	Direction of abnormality
Hematology				
Platelets	Platelets count	PLAT	Platelet count decreased	Low
Red blood cells	Hemoglobin	HGB	Anemia/Hemoglobin increased	Low/High

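### Follow-up laboratory summaries and, by a narrower route, the late-toxicity outputs do not distinguish findings made after adjuvant chemotherapy has started

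*Protocol*

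**What the plan says.** **Exposure.** Protocol Section 1.3, Table 2: "Adjuvant chemotherapy if given, according to local guidelines, must start between 1 and 3 mo after surgery". Section 6.5 adds: "The following adjuvant chemotherapies are allowed: FOLFOX and CAPEOX or capecitabine as per NCCN 2019 guidance". Capecitabine is therefore both a study intervention and a permitted adjuvant drug. Recipients remain on the protocol schedule (Section 4.1.3), with AE assessment, hematology and serum chemistry at Weeks 21, 27, 39 and 52 (Table 2).

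**AE recording.** Under Protocol Section 8.3.1, unrelated AEs are recorded only through short-term follow-up (to about Week 19) and unrelated SAEs only to Week 27. Related events have no such limit.

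**Late toxicity.** SAP Section 15.2.3 counts as late any new, recurrent or worsened AE that starts after the on-treatment period. The outputs are a "Table of all late toxicities by worst CTCAE grades" and two listings, one of events related to trial treatment and one of Grade 3 or higher. None carries a condition on adjuvant therapy.

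**Laboratory data.** SAP Section 15.4 says: "Listings and summaries by visit will include all assessments". Shift tables and worst-value summaries stop at the end of the on-treatment period. SAP Section 9 makes presentation by dose level and overall the default, and limits by-visit displays through a rule requiring at least 3 participants.

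**Adjuvant treatment itself.** SAP Section 12.4: "Subsequent anti-cancer treatments will be listed according to eCRF pages". No table counts recipients.

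**The concern.** The protocol keeps one year of follow-up in order to see late radiotherapy effects. Protocol Section 2.3 places these at 3 months or more after RT, which is close to the time when adjuvant chemotherapy may begin. A blood count or chemistry value taken during or after FOLFOX or CAPEOX then appears in the same by-visit row as one from a participant who had no further treatment, under a peposertib dose label. Whether a participant receives adjuvant therapy depends on local guidelines and not on the assigned dose. With a planned cohort size of 3, a chance imbalance in recipients between dose levels could look like a dose pattern or mask one. The planned outputs would not show the reader that this had happened.

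**Working it through.** **1. The plan's own timeline.** Protocol Section 4.1.3 states that "the duration of the Short-term Safety Follow-up is approximately 13.5 to 14 weeks after treatment completion", and puts surgery at Week 15, about 9.5 weeks after RT. Treatment lasts 5 to 5.5 weeks.
- Week 19 − 5.5 = 13.5 weeks; Week 19 − 5 = 14 weeks. Reproduced.
- Week 15 − 5.5 = 9.5 weeks. Reproduced.

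**2. When adjuvant therapy can start.** The SAP Section 9 conversion gives 1 month = 30.4375/7 = 4.35 weeks, so 3 months = 13.04 weeks.

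| Surgery | Start at 1 month | Start at 3 months |
|---|---|---|
| Week 13 (−14 days) | 17.35 | 26.04 |
| Week 15 | 19.35 | 28.04 |
| Week 17 (+14 days) | 21.35 | 30.04 |

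**3. Share of long-term follow-up after adjuvant start.** The period from Week 19 to Week 52 is 33 weeks.
- Surgery at Week 15: (52 − 28.04)/33 = 72.6% to (52 − 19.35)/33 = 98.9%.
- Over the surgery window: (52 − 30.04)/33 = 66.5% up to 100%.

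This is time after start, not time on chemotherapy.

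**4. Time on chemotherapy.** The documents give no duration. For assumed courses with surgery at Week 15: 12/33 = 36%, 16/33 = 48%, 20/33 = 61%, and 24 weeks gives 73%. More than half of the period is covered only if the course exceeds 33/2 = 16.5 weeks.

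**5. Laboratory route.** Visits at Weeks 21, 27, 39 and 52 all have hematology and chemistry, and by-visit summaries take every assessment. With surgery at Week 15 and an assumed 12-week course, a start at 1 month puts Weeks 21 and 27 on chemotherapy, and a start at 3 months puts Week 39 on it. The mixing is direct.

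**6. AE route.** An event attributed to adjuvant therapy alone is unrelated to study intervention. It reaches the late-toxicity outputs only in these ways:
- As an unrelated SAE up to Week 27. With surgery at Week 15 the exposed window is at most 27 − 19.35 = 7.7 weeks and may be zero; with surgery at Week 13 it is at most 27 − 17.35 = 9.7 weeks.
- As a non-serious AE around the Week 19 visit. With surgery at Week 13 the overlap is up to 19 − 17.35 = 1.7 weeks. With surgery at Week 15 it is nil at Week 19 exactly, and up to 21 − 19.35 = 1.7 weeks if the visit falls at +14 days.
- As an event attributed to study intervention. SAP Section 15.2 also counts a missing or unknown relationship as related.

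**7. What lies outside.** The on-treatment period ends 30 days after last dose: 5 + 30/7 = Week 9.3, or 5.5 + 30/7 = Week 9.8. The earliest adjuvant start is Week 17.3. DLTs, TEAE tables and the SAP's shift and worst-value tables are therefore untouched. Adjuvant drugs also fall outside the concomitant-medication summaries (SAP Section 12.2), so no table shows who received them.

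**8. Size.** One participant is 1/3 = 33.3 points in a dose level of 3, and 1/19 = 5.3 points among the 19 treated as of 06 May 2021.

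**The case against.** The case for leaving the plan alone has real weight.

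- The analyses are exploratory (Protocol Section 9.1), escalation has stopped and Phase II will not start, so no decision in the documents rests on a late-toxicity dose trend. This stands and keeps the point minor.
- Any single event moves a cohort of 3 by 33 points, whatever its cause. This also stands: the figure shows how fragile these cohorts are and does not measure bias.
- With 19 participants, a reader can compare listings. This stands in part. The AE listings give dosing dates for the three study interventions only, so the adjuvant listing must be matched by hand, and the summaries stay mixed.
- The 3-participant display rule may suppress late visits by dose level. That is true, but the overall column is less likely to be affected.
- Splitting cohorts of 3 would leave nearly empty panels. This stands, and argues for a flag instead of separate panels by dose level.

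Three stronger readings are tempting, and the documents do not support them.

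- A reader might infer that chemotherapy covers most of follow-up. That needs a course longer than 16.5 weeks, and no duration is given.
- A reader might infer that adjuvant therapy lets a true late radiotherapy effect be called unrelated and go unrecorded, since Appendix 7 says of unrelated events: "A reasonable alternative explanation must be available". That is an additional requirement. The event must also be one that could not medically be attributed to study intervention.
- A reader might infer that the capecitabine causality item cannot tell study use from adjuvant use. The CRF is not in the documents, and Appendix 7 ties relatedness to the intervention under study in this protocol. Only possible misattribution by an investigator remains.

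**Conclusion.** The point holds as a minor one. The by-visit hematology and chemistry summaries at Weeks 21 to 52 mix values from before and after adjuvant start, by peposertib dose level and overall, subject to the display rule. The late-toxicity table and listings can contain adjuvant-period events, by the narrow route in step 6. For a recipient operated on at Week 15, 73% to 99% of Weeks 19 to 52 follows adjuvant start; the share on chemotherapy is 36% to 73% if courses last 12 to 24 weeks, which is an assumption. The number of recipients is not given, so the actual effect cannot be sized. The exemption of the laboratory worst-value tables rests on the SAP. Protocol Table 13 speaks of worst grades on study, which read literally would reach into the adjuvant period.

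**What to change.** Derive one yes/no flag: onset or sample on or after the first adjuvant dose. The inputs exist. Protocol Section 6.5 has concomitant therapies recorded with dates until study completion, and SAP Section 9 already uses dates of anti-cancer treatment after discontinuation.

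- **SAP 15.2.3:** add the flag, adjuvant start date and regimen to both late-toxicity listings. In the late-toxicity table, show how many participants had onset on or after adjuvant start.
- **SAP 15.4:** in the overall by-visit summaries after Week 19, show values on or after adjuvant start separately. By dose level, flag them in the listings only.
- **SAP 12.4:** tabulate adjuvant recipients by dose level.

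The cost is SAP wording, a little programming and small counts in some cells. SAP Section 9 imputes a missing start day as the last day of the month, unless the therapy ended earlier. This could place some adjuvant-period values before the start, so imputed dates should be marked. The flag shows time after the first dose, not time on treatment, and the table footnote should say so.

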2.2 Background

Peosertib is a novel, potent, and selective ATP-competitive inhibitor of DNA-PK that targets tumor cell growth and survival by inhibiting the critical DNA damage repair mechanism in solid and hematological malignancies. DNA-protein kinase with its protein subunits, kilo units 70 and 80, regulates one of the major pathways responsible for repair of DSBs in DNA caused by RT or chemotherapeutic agents (Curtin 2012). The activity of DNA-PK is critical for successful DSB repair via the nonhomologous end joining mechanism.

The antitumor effect of peposertib is dependent on the functionality of DNA repair and checkpoint signaling in cancer cells, which have a lowered ability to cope with DSBs in their DNA and frequently undergo apoptotic cell death (Furgason 2013). Hence, one rationale of DNA-PK inhibition is to potentiate the effect of DNA damage generated by RT.

CCI

The clinical development of peposertib comprises 3 studies using the capsule formulation. The first-in-man study (EMR100036-001) initiated in participants with advanced solid tumors

completed the single dose escalation part where 31 participants were treated with dose levels between 100 mg once daily and 400 mg twice daily. The maximum tolerated dose (MTD) was not reached at 400 mg twice daily; however, further dose escalation was not done, per Safety Monitoring Committee (SMC) decision. There were no dose limiting toxicities (DLTs) reported at the 400 mg twice daily dose level. The recommended Phase II dose (RP2D) for peposertib monotherapy was established as 400 mg twice daily and confirmed in an additional 6 aspirin-naïve participants (aspirin-naïve participants were included to test for alterations in platelet aggregation). The efficacy data did not support further development of peposertib in monotherapy due to the lack of clear clinical activity in this setting.

The second study with peposertib (EMR100036-002) is currently ongoing and is a combined Phase Ia/Ib, open label, dose escalation and dose-expansion study designed to explore the safety, tolerability, PK, CCI and clinical activity of peposertib in combination with RT/chemoradiotherapy (CRT), and to determine the MTD and a RP2D for peposertib in combination with RT/CRT.

- The Arm A-Phase Ia part of the study includes previously treated participants with locally advanced disease (any tumor or metastases including lymphomas) localized in the head and neck region or thorax that is not amenable to surgical therapy or with standard systemic therapy with an indication for palliative RT (30 Gy in 10 fractions) over 2 weeks.
- The Arm B-Phase Ia part includes treatment naïve SCCHN participants who are eligible for fractionated RT (66 to 70 Gy in 33 to 35 fractions) with concurrent cisplatin.
- In ancillary clinical proof-of-principle part of the study, participants with at least 2 cutaneous/subcutaneous tumors/metastasis are included to evaluate alterations in phosphorylated-DNA-PK expression induced by RT (Lesion 1), as compared with expression induced by RT after administration of peposertib (Lesion 2).

A third study (MS100036-0022) investigated peposertib in combination with etoposide and cisplatin in participants with treatment naïve extensive disease SCLC. Two participants were treated with peposertib (capsule and tablet formulation). One participant received a single dose of the tablet, and the capsule for the remainder of the study. No DLTs or deaths were reported, and none of the participants discontinued due to an adverse event (AE). Enrollment in the study was prematurely terminated due to recruitment challenges and not due to concerns of safety for the subjects.

The Investigator's Brochure provides a more detailed overview of the nonclinical and clinical information on peposertib.

Rectal cancer is a subset of colorectal cancer, which is the third most common diagnosed cancer. An estimated 40,000 new cases of rectal cancer were diagnosed in 2017 in the USA with an increase in incidence rates in the younger population (Siegel 2017). In the European Union the incidence of rectal cancer is 15 to 25 cases/100,000 population per year resulting in approximately 125,000 new cases per year, and mortality is 4-10/100,000 population per year (Glynn-Jones 2017). Rectal cancer is a distal large bowel adenocarcinoma tumor located at or below the peritoneal reflection. The standard of care (SoC) for locally advanced rectal cancers is neoadjuvant CRT, with or without sequential chemotherapy followed by surgical intervention (e.g.

total mesorectal excision [TME]), with the aim to remove the irradiated tumor and decrease the risk of local recurrence and mortality (National Comprehensive Cancer Network® [NCCN] Guidelines for Patients® Rectal Cancer 2019; Glynne-Jones 2017). This methodology has resulted in a decrease in local recurrence and an improvement in mortality rates (Shahab 2017). However, one-third of patients with locally advanced rectal cancer will later develop distant metastases and will subsequently die from the disease. In addition, most survivors experience significant impairment in their QoL, due primarily to removal of the rectum. Consequently, the current challenges in the treatment of locally advanced rectal cancer are how to improve survival by reducing the risk of distant metastases, and how to improve QoL in surviving patients by preserving the rectum. There is an unmet need to improve long-term outcomes and QoL and so the development of new therapeutic strategies to further increase these aspects is of key importance.

